5.1. Inclusion Criteria

Participants are eligible to be included in the study only if all of the following criteria apply:

1. Male and female children aged ≥ 2 years to < 12 years (at the screening visit).
2. Diagnosis of AD as defined by the Hanifin and Rajka (1980) criteria.
3. AD duration of at least 3 months (participant/parent/guardian may verbally report signs and symptoms of AD with onset at least 3 months prior).
4. IGA score of 2 to 3 at the screening and baseline visits.
5. %BSA (excluding the scalp) with AD involvement of 3% to 20% at the screening and baseline visits.
6. For children aged 6 years to < 12 years, baseline itch NRS score ≥ 4 (see Section 8.2.7).
Note: Participants who are aged 6 years to < 12 years must record Itch NRS scores for at least 4 of the 7 days immediately prior to the Day 1/baseline visit.
7. Participants/guardians who agree to discontinue all agents used by the participant to treat AD from the screening visit through the final safety follow-up visit.
8. For participants who sign photography consent, at least 1 target lesion that measures at least 5 cm² at the screening and baseline visits. The target lesion must be representative of the participant's disease state but not located on the hands, feet, or genitalia.

9. For sexually active participants, willingness to take appropriate contraceptive measures (see [Appendix A](#)) to avoid pregnancy or fathering a child for the duration of study participation with the exception of male and female participants who are prepubescent.

Note: Female participants who have reached menarche must have a negative urine pregnancy test at the screening and baseline visits before the first application of study cream on Day 1. They must also take appropriate precautions to avoid pregnancy from the screening visit through the safety follow-up visit.

10. Ability to comprehend and willingness to sign an ICF or written informed consent of the parent(s) or legal guardian and a verbal or written assent from the participant when possible.

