Rationale for change: The evaluable population for the key secondary endpoint (proportion of participants with a \geq 4-point improvement in Itch NRS score from baseline to Week 8) requires participants 6 years of age or older who have nonmissing baseline Itch NRS scores. It was discovered that this subgroup was under-enrolled at a time when the overall enrollment was close to final. Based on the enrollment status on 14 JUL 2022, among 255 participants screened, approximately 116 participants were qualified in that subgroup. To ensure enough power for this key secondary endpoint, at least 180 participants are required in this subgroup, and to achieve that the overall population will be increased from 250 to 315.

The sample size calculation of 180 in this subgroup is based on the results from the 2 pivotal studies, INCB 18424-303 and INCB 18424-304, in which the response rate for the key secondary endpoint at Week 8 is assumed to be 52% and 42% for the active arms (ruxolitinib 1.5% cream BID and ruxolitinib 0.75% cream BID, respectively) versus 16% for vehicle cream BID. Using a 2-sided alpha of 0.025, the sample size will have $> 90\%$ power to detect a difference between ruxolitinib 1.5% cream BID versus vehicle cream BID and 70% power to detect a difference between ruxolitinib 0.75% cream BID versus vehicle cream. In addition to providing adequate power for all efficacy variables, the sample size increase is also providing a larger database for safety evaluation.

2. Section 1, Protocol Summary (Table 3: Schedule of Activities: Vehicle-Controlled Period); Section 5.1, Inclusion Criteria (Inclusion Criterion 8); Section 8.2.3, Target Lesion Identification; Section 8.2.4, Photography

Description of change: Instructions were added such that only participants who are participating in photography are required to identify and measure target lesions at the screening and baseline visits. For participants not participating in photography, the identification and measurement of target lesions are optional.

Rationale for change: Clarification was added that only participants who are participating in photography are required to identify and measure target lesions.

3. Section 5.1, Inclusion Criteria (Inclusion Criterion 6); Section 8.2.7, Itch Numerical Rating Scale

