To control the overall Type I error rate, 2-sided $\alpha = 0.05$, the Bonferroni's method will be used. In Step 1, within Family 1 and 2, the endpoints are tested in a fixed sequence at a Bonferronized 2-sided $\alpha = 0.025$ level. The key secondary endpoint will be tested only if the associated primary endpoint is rejected. For any treatment strength, if the 2 related null hypotheses can be rejected, then the fixed sequence for the other treatment strength can be conducted at the 2-sided $\alpha = 0.05$ level. If all null hypotheses in Family 1 and 2 are rejected, in Step 2, the endpoints in Family 3 (H13 and H23) will be tested using Bonferroni-Hochberg's procedure with overall 2-sided $\alpha = 0.05$ level. If both hypotheses in Family 3 are rejected, the endpoints in Family 4 (H14 and H24) will be tested similarly using Bonferroni-Hochberg's procedure with overall 2-sided $\alpha = 0.05$ level. The approach is visualized in [Figure 2](#).

Figure 2: Control of Overall Type I Error Rate

Step 1:

Step 2:

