7.2.2. Primary Efficacy Analyses

The primary analysis will be based on the ITT population in the VC period. The primary alternative hypothesis (superiority of ruxolitinib 1.5% BID or 0.75% BID compared with vehicle) will be tested using logistic regression. This model will include the treatment group (1.5% BID, 0.75% BID, and vehicle) and stratification factors (baseline IGA score and age). The unadjusted p-values between each treatment group versus vehicle will be calculated based on the Wald test, which will be compared with the procedure defined in Section 3.2. Exact logistic regression ([Mehta and Patel 1995](#)) will be used for all of the comparisons if any of the dose levels have an expected cell count < 5 .

The odds ratio and 95% CI at Week 8 for the response rates (ruxolitinib cream/vehicle) will be computed for the above model. Additionally, the difference in IGA-TS response rates (ruxolitinib cream – vehicle) at Week 8 will be computed. The 95% CI for the difference will be computed based on a large-sample normal approximation with continuity correction.

All nonresponders during the VC period, as well as all participants missing the Week 8 assessment and who discontinue study treatment at any time before Week 8, or discontinue from the study for any reason, will be defined as nonresponders for the nonresponder imputation analysis.

The primary outcome will also be examined for the PP population using the same model as the primary analysis.

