7.3. Analysis of the Key Secondary Efficacy Parameters

7.3.1. Key Secondary Efficacy Measures

7.3.1.1. Itch Numerical Rating Scale Score

The Itch NRS is a once-daily patient-reported measure of itch intensity assessed using an 11-point scale (0 = no itch to 10 = worst imaginable itch). Participants aged 6 years or older will be asked to record their highest (worst) level of itch in the evening over the 24-hour recall period.

The Itch NRS score for baseline will be determined by averaging the 7 daily NRS scores directly before Day 1 (Day -7 to Day -1) for all the by-visit summaries. The by-visit Itch NRS score for postbaseline visits will be determined by averaging the 7 daily NRS scores directly before the visit day. If 4 or more daily scores are missing (out of the 7), the Itch NRS score at the visit will be set to missing. For all daily itch related analyses, including time to achieve Itch NRS score improvement of at least 2 or 4 points analyses, baseline will be defined as the last available Itch NRS score during the week prior to Day 1 (Day -7 to Day -1).

The proportion of participants with a clinically relevant change in itch, defined as a ≥ 4 -point improvement in by-visit or daily Itch NRS score from baseline, will be summarized by treatment group for participants with baseline Itch NRS score ≥ 4 .

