7.3.2. Key Secondary Efficacy Analysis

Key secondary efficacy analyses will be conducted in the ITT population in the VC period. If the primary objective is achieved, the statistical comparisons for key secondary endpoints will be tested with the procedures specified in Section 3.2.

The same nonresponder imputation method as specified in the primary analysis will be used to handle missing Week 8 itch data, and the logistic regression described in Section 7.2.2 will be applied to compare each ruxolitinib cream group and the vehicle cream group for the key secondary endpoint of ≥ 4 -point improvement in Itch NRS score response at Week 8.

For the key secondary endpoints of Itch NRS score responses on Day 7 (Week 1) and Day 3, all participants who are missing Day 7 and/or Day 3 daily Itch NRS scores will be imputed using multiple imputation by fully conditional specification method. The variables to be included in the imputation regression model are treatment group, stratification factor, baseline itch score, and postbaseline daily itch score on Day 1 to Day 7. The corresponding binary response on Day 7 and Day 3 will be derived for each of the imputed datasets per the definition in Section 7.3.1.1. The logistic regression specified in Section 7.2.2 will be applied to each imputed dataset and then the results will be combined for the inference using Rubin's rule.

The following sample SAS code will be used for the MI:

```
proc mi data=mi_wide seed=18424 n impute=30 out=impute_itch;
  class trt01p strat1 strat2;
  var trt01p strat1 strat2 base avald1 avald2 avald3 avald4 avald5
  avald6 avald7;
  fcs regpmm nbiter=30;
run;
```

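### The Week 8, Day 7 and Day 3 itch responder tests leave out baseline Itch NRS, a score every analysed child has; adding it is a free efficiency improvement of uncertain, probably modest size

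*SAP*

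**What the plan says.** SAP 7.2.2 defines the logistic model for IGA-TS: "This model will include the treatment group (1.5% BID, 0.75% BID, and vehicle) and stratification factors (baseline IGA score and age"). SAP 7.3.2 carries it over to the key secondary endpoints. For Week 8 itch, "the logistic regression described in Section 7.2.2 will be applied to compare each ruxolitinib cream group and the vehicle cream group". For Day 7 and Day 3, "The logistic regression specified in Section 7.2.2 will be applied to each imputed dataset". Protocol 10.4.2 agrees.

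Baseline itch appears in one place only, the imputation model for Day 1 to Day 7, whose variables are "treatment group, stratification factor, baseline itch score, and postbaseline daily itch score on Day 1 to Day 7". It is not in the model that produces the test.

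The score exists for every child in these analyses. Under Protocol 5.1, criterion 6, children aged 6 to under 12 need a baseline Itch NRS of at least 4 and "must record Itch NRS scores for at least 4 of the 7 days immediately prior to the Day 1/baseline visit". SAP 7.3.1.1 says that the responder proportion "will be summarized by treatment group for participants with baseline Itch NRS score" of 4 or more. Appendix A (Tables 2.3.1 and 2.3.6) applies the same threshold, using the daily baseline for Day 1 to Day 7.

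On alpha, SAP 3.2 starts each strength at two-sided 0.025 and then recycles, which raises the level to 0.05: "For any treatment strength, if the 2 related null hypotheses can be rejected, then the fixed sequence for the other treatment strength can be conducted". Step 2 (Day 7, then Day 3) opens only if all four Step 1 hypotheses are rejected.

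**The concern.** A response is a drop of at least 4 points on a 0-10 scale. A child who starts at 4 has to reach 0; a child who starts at 8 has to reach 4. That arithmetic makes baseline itch a natural prognostic covariate for this endpoint.

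The planned covariates were chosen for IGA-TS and may do little for itch. The age strata are 2-6 and 7 to under 12 years (SAP 3.1), while itch is collected only from age 6 (Protocol 8.2.7). In the itch set, the age factor therefore only separates 6-year-olds from older children. Randomisation is not stratified by itch.

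What is at stake is power where the hierarchy has least to spare among the tests with a stated power. The Amendment 5 rationale (Protocol Appendix F) gives 70% for 0.75% versus vehicle on Week 8 itch (H22). If H22 fails, H13, H23, H14 and H24 are never tested.

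**Working it through.** **Inputs from the documents.** Amendment 5 rationale: at least 180 children in the itch subgroup; response 52% (1.5%), 42% (0.75%) and 16% (vehicle). It states "Using a 2-sided alpha of 0.025, the sample size will have" more than 90% power for 1.5% and 70% for 0.75%. With 2:2:1 allocation, 180 children give 72/72/36.

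**Reproducing the stated power.** Pooled normal approximation: power = Φ[(|p1 − p0| − z·s0)/s1], where s0 is the pooled and s1 the unpooled standard error, and z = 2.241 for two-sided 0.025.

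- 0.75%: pooled rate (72 × 0.42 + 36 × 0.16)/108 = 0.333, s0 = 0.0962, s1 = 0.0844. (0.26 − 2.241 × 0.0962)/0.0844 = 0.525, so power is 70.0%.
- 1.5%: pooled rate 0.40, s0 = 0.100, s1 = 0.0849. (0.36 − 0.2241)/0.0849 = 1.60, so power is 94.5%.

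Both stated figures reproduce. Fisher's exact test gives 67.7% and 93.6%; the rationale does not name its test. For comparison, the same approximation gives 99.9% and 99.6% for the two IGA-TS tests at 126 versus 63. At alpha 0.05, H22 has 80.1%.

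**Assumptions needed beyond the documents.** Baseline itch is taken as truncated to 4-10 with mean about 6.5 and SD about 1.4. Its association with response is varied as an odds ratio (OR) per NRS point, holding the marginal rates at 52/42/16%. Simulated trials (3,000-4,000 per scenario) were analysed with the planned three-arm Wald test, with and without baseline itch.

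**Recycling rule.** With both IGA-TS hypotheses taken as rejected, H12 and H22 are both rejected if one has p ≤ 0.025 and the other p ≤ 0.05.

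**Results at 72/72/36, planned model → with baseline itch (%).**

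| OR per NRS point | H12, alpha 0.025 | H22, alpha 0.025 | H12 and H22 both, with recycling |
|---|---|---|---|
| 1.0 | 94.0 → 93.9 | 70.0 → 69.8 | 77.4 → 77.1 |
| 1.2 | 93.1 → 93.0 | 67.7 → 68.5 | 77.6 → 78.1 |
| 1.35 | 93.4 → 94.5 | 68.3 → 70.2 | 79.5 → 80.8 |
| 1.5 | 93.4 → 95.0 | 68.9 → 71.7 | 79.1 → 81.1 |
| 1.75 | 93.4 → 95.8 | 69.0 → 74.9 | 78.7 → 82.4 |
| 2.0 | 94.4 → 97.0 | 68.6 → 78.0 | 77.3 → 83.6 |

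The Monte Carlo standard error is about √(0.69 × 0.31/4000) = 0.7 points, so differences between rows within the planned-model figures are noise. Separate runs put the top of the H22 column at 76-78%.

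**A different response model.** If the follow-up score is regressed on baseline, the H22 change depends on the slope: 67.5 → 72.7% at slope 0.3, 70.2 → 73.0% at 0.5, 68.5 → 69.3% at 0.7, and no gain at 1.0, where follow-up tracks baseline one for one.

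**A smaller itch set.** At 58/58/29, an assumption below the stated target, the chance of rejecting both goes from 67.6 to 69.9% (OR 1.5), 66.3 to 71.6% (OR 1.75) and 66.7 to 74.3% (OR 2.0).

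**Type I error.** With all arms at 16% and a two-sided 0.025 test, rejections in favour of active occurred in 0.2-0.4% of trials under either model, against a nominal 1.25% in that direction.

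**Day 7 and Day 3.** The documents state no early response rates. Purely as illustration, invented rates of 30/25/10% give gains of about 2 points at OR 1.35 and 5-6 points at OR 1.75.

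**The case against.** The planned model is valid. It adjusts for both stratification factors, Protocol and SAP agree on it, and its type I error is controlled. Which further covariate to prespecify is a design choice. All of that stands, and it is why this is an improvement and not an error.

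The size of the gain rests on assumptions. That also stands: with no association there is nothing to gain, and at OR 1.2 the gain is under 1 point.

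Some stronger readings are tempting but not supported:

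- **That a low baseline bars some children from responding.** It does not. The analysis is limited to baseline 4 or more, so a 4-point drop is possible for everyone analysed.
- **That chance imbalance in baseline itch biases the result.** With an assumed SD of 1.35, an active-vehicle difference of at least 0.5 points arises in about 7% of trials at 72 versus 36. At OR 1.5 this shifts the odds by 1.5^0.5 = 1.22. The unadjusted test's error rate already allows for such imbalance; adjustment reduces the noise.
- **That Step 2 has only a 68-70% chance of opening.** That is H22 at 0.025 alone. H12 has about 94% power, so H22 is usually tested at 0.05, and the joint chance is about 78%.
- **That H12 is among the weak tests.** Its stated power is above 90%.
- **That 29 vehicle children should be expected.** No document says so; the target of 180 implies 36.

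**Conclusion.** The omission is plain in both documents, and including baseline itch would be a free improvement. At the sponsor's rates and 72/72/36, H22 power at alpha 0.025 goes from about 68-70% to between 68% and 76-78%. The chance of rejecting both Week 8 itch hypotheses under recycling goes from about 78% to 78-84%: nil at OR 1.0, about 2 points at OR 1.5, about 6 at OR 2.0 per NRS point. If only 58/58/29 were analysed, that chance goes from about 66% to 66-74%.

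These figures depend on an assumed baseline distribution and association. Confidence is high that the covariate is missing and that adding it does no material harm, and moderate on the size of the gain. For Day 7 and Day 3 no gain can be quantified from the documents. A reader should not infer that the planned itch tests are biased or invalid.

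**What to change.** Before unblinding, add baseline Itch NRS as a continuous covariate to the itch logistic models in SAP 7.3.2 and Protocol 10.4.2, and to the itch responder model in SAP 7.4.2.1. Use the baselines SAP 7.3.1.1 already defines: the 7-day mean for by-visit endpoints, and the last available daily score in the week before Day 1 for Day 7 and Day 3. If the Protocol is not amended, record the change in SAP 11.1, which at present lists none.

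State what happens if the exact logistic fallback is triggered, because a continuous covariate can leave the exact conditional distribution close to degenerate. Either keep the planned covariates or use baseline itch in prespecified categories.

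The cost is a few lines of text and no new data. The one real consequence is interpretive: the itch odds ratio becomes conditional on baseline itch as well as on IGA and age.

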7.4. Analysis of Secondary Efficacy Parameters

7.4.1. Secondary Efficacy Measures

7.4.1.1. Eczema Area and Severity Index Score

Atopic dermatitis will be assessed using the EASI scoring system, which is a validated scoring system that grades the physical signs of AD to provide a measure of AD severity (ranging from 0 to 72).

The weight of the body regions for the EASI scoring is based on age (< 8 years or \geq 8 years):

- For participants 8 years of age or older: head/neck (H) = 0.1, upper limbs (UL) = 0.2, trunk (T) = 0.3, and lower limbs (LL) = 0.4
- For participants 7 years or younger: head/neck (H) = 0.2, upper limbs (UL) = 0.2, trunk (T) = 0.3, and lower limbs (LL) = 0.3

Each of the 4 body regions is assessed separately for erythema (E), induration/papulation/edema (I), excoriations (Ex), and lichenification (L) for an average degree of severity of each sign in each region with 0 = none, 1 = mild, 2 = moderate, and 3 = severe, with half-steps allowed.

The disease severity strata for the EASI are as follows: 0 = clear; 0.1 to 1.0 = almost clear; 1.1 to 7.0 = mild; 7.1 to 21.0 = moderate; 21.1 to 50.0 = severe; and 50.1 to 72.0 = very severe.

The categorical variable EASI75 to indicate the EASI responder will be set to 1 for percentage improvement from baseline in EASI score of 75% or greater and will be equal to 0 for percentage improvement of less than 75%. [REDACTED]

7.4.2. Secondary Efficacy Analysis

All secondary efficacy analyses will be conducted based on the ITT population in the VC period.

7.4.2.1. Categorical Efficacy Endpoints

For the following categorical parameters, summary statistics including sample size, frequency, and percentages will be presented by visit:

[figure not shown]
- Proportion of participants achieving an IGA-TS
- Proportion of participants with a \geq 4-point improvement in Itch NRS score
- Proportion of participants achieving EASI75

[figure not shown]
A logistic regression model with treatment and stratification factors as covariates will be fit at Week 8. The p-values between each ruxolitinib group versus vehicle will be calculated based on the Wald test. Exact logistic regression will be used for all of the comparisons if any of the dose levels have an expected cell count < 5 . The NRI will be used to impute postbaseline missing values for binary outcomes based on IGA, Itch NRS, and EASI scores.

[figure not shown]
7.4.2.2. Time-to-Event Efficacy Endpoints

[figure not shown]
For the time to achieve Itch NRS score improvement of at least 2 or 4 points, a log-rank test stratified by randomization stratification factors will be used for between-treatment group comparisons. The hazard ratio and its 95% CI will be estimated based on the stratified Cox regression model using Efron's method accounting for ties. Kaplan-Meier curves will be presented by treatment group. The number of participants, number of events, and number of censoring will be summarized by treatment group. The Kaplan-Meier estimate of median time will be presented with its 95% CI. The 95% CI will be calculated using the method by Brookmeyer and Crowley (1982).

[figure not shown]

[figure not shown]

[figure not shown]

9. SAFETY AND TOLERABILITY

[Appendix A](#) provides a list of planned tables figures, and listings. Sample data displays are included in a separate document.

9.1. General Considerations

The analyses in this section will be provided for the safety population in the VC period and for the LTS evaluable population in the LTS period. Cumulative TEAEs across the treatment periods (VC and LTS periods) will be summarized. Summary tables may be replaced with listings when appropriate. For instance, an AE frequency table may be replaced with a listing if it only contains a few unique PTs reported on relatively few participants.

9.2. Adverse Events

9.2.1. Adverse Event Definitions

A TEAE is any AE either reported for the first time or worsening of a pre-existing event after first application of study drug and within 30 days after the last dose of study drug. For participants who cross over treatments, the first application date is period specific, and the end date is 30 days after the last application date in this period or the first application date in the next period, whichever comes first. Analysis of AEs (as discussed below) will be limited to TEAEs, but data listings will include all AEs regardless of their timing in relation to study drug administration.

Adverse events will be tabulated by MedDRA PT and SOC. Severity of AEs will be graded using the NCI CTCAE v5. The CTCAE (Grade 1 to 5) is used for this study. The CTCAE reporting guidelines and grading details are available on the Cancer Therapy Evaluation Program website.

The subset of AEs considered by the investigator to be related to study drug will be considered treatment-related AEs. If the investigator does not specify the relationship of the AE to study drug, the AE will be considered treatment-related. The incidence of AEs and treatment-related AEs will be tabulated. In addition, serious AEs will also be tabulated.

Any missing onset date, causality, or severity must be queried for resolution. Unresolved missing causality and severity will be handled according to the following rules:

- An unresolved missing causality will be considered treatment-related.
- An unresolved missing severity will be identified as an unknown severity.

For purposes of analysis, all AEs will be considered TEAEs unless the AE can unequivocally be defined as not treatment-emergent.

Application site reactions are AEs that occur at the site of drug application. A summary of ASRs will be provided. Exposure-adjusted summaries will also be provided for the safety population, including cumulative TEAEs and cumulative ASRs.

